9.2.3 Tumor Specimen Processing

Biopsy cores will be processed as described in NCI DCTD SOP340507. All external sites are required to follow NCI DCTD SOP340507 for biopsy collection, processing, and shipment; the SOP can be found by following the link below.

http://dctd.cancer.gov/ResearchResources/biomarkers/docs/par/SOP340507_Biopsy_Frozen.pdf

A webinar training session with PADIS staff will be held with each participating site prior to their first biopsy collection to review proper procedure. The sites should contact [contact] to initiate training and clarify shipping procedures.

Dermatologic and ENT biopsies should be collected per guidance from FNLCR PD Central Receiving ([contact], [contact], or [contact]).

Briefly, the biopsy cores (up to 5 per time point) or equivalent tissue, will be individually transferred into 1.5-mL pre-chilled cryovials and then flash frozen in liquid nitrogen. In accordance with SOP340507, biopsy specimens are collected into pre-chilled 1.5-mL Sarstedt, O-ring screw cap tubes (VWR, Cat#: 83009-010) and then flash-frozen in liquid nitrogen or a dry ice/ethanol bath. It is **imperative** that biopsies are flash frozen *within 2 minutes of collection* in order to preserve key pharmacodynamic biomarkers.

9.2.4 Baseline and C3D1 Biopsy Specimens

The frozen **baseline** and **C3D1** biopsy specimens are transferred to PADIS in pairs on dry ice, where they are stored at -80°C or colder, and subsequently processed within 7-10 days for analysis or as directed by the Principal Investigator. Biopsy samples will be analyzed as described above; any additional samples will be kept for future analysis in the Frederick National Laboratories CR Biorepository in liquid nitrogen freezers. Additional studies, if performed, will be conducted following an amendment to the current protocol.

Biopsy specimens should be labeled with:

- Sample type (e.g., Biopsy)
- Time point (e.g., C01D01 pre dose)
- Collection date and time
- Sample ID, containing:
 - CTEP protocol number
 - Unique patient ID (Do NOT include patient name, medical record number, or initials)
 - 500-series sample collection number (e.g., 500, 501, 502, etc.)
 - Pass/Core identifier (e.g., A, B, C, etc.)

For example, the sample ID for the first core of a baseline sample collected for NCI DTC

patient #004 should be: 10398_NCIDTC_004_500A.

9.2.4.2 Shipping Baseline and C3D1 Biopsy Specimens from the NIH Clinical Center

For NIH Clinical Center specimens only: Baseline and post-treatment biopsy samples should be held at -80°C or colder and shipped to PADIS together upon completion of the second biopsy. Shipment should be by CSP Courier and may be arranged by contacting [name], FNLCR, [contact]. Non-NIH sites should not contact this number; please contact NCI PD Support as described in Section [9.2.4.1](#).

9.2.5 **Optional Restaging Follow-Up or Progression Biopsy Specimens**

Biopsies will be collected and flash frozen as above (Section [9.2.3](#)).

The sample shipping manifest and batch record, both of which are included in NCI DCTD [SOP340507](#), should be completed and included with the shipment. NCI DCTD SOP340507 for biopsy collection, processing, and shipment; the SOP can be found by following the link below.

http://dctd.cancer.gov/ResearchResources/biomarkers/docs/par/SOP340507_Biopsy_Frozen.pdf

Biopsy specimens should be labeled with:

- Sample type (e.g., Biopsy)
- Time point (e.g., Restaging)
- Collection date and time
- Sample ID, containing:
 - CTEP protocol number
 - Unique patient ID (Do NOT include patient name, medical record number, or initials)
 - 500-series sample collection number (e.g., 500, 501, 502, etc.)
 - Pass identifier (e.g., A, B, C, etc.)

For example, the sample ID for the first core of a restaging follow-up sample collected for NCI DTC patient #004 should be: 10398-NCIDTC-004-502A (if C1D1 and C3D1 were already collected as 500 and 501, respectively).

9.3 Correlative Assays in Blood

9.3.1 Genetic Analysis – All Sites

Blood collection for genetic analysis is mandatory at all sites for patients ≥ 12 years of age.

9.3.1.1 Blood Collection for Genetic Analysis (Performed at All Sites)

Two whole blood samples (at least 7.5 mL each in 10-mL Streck tubes) will be collected at each of the following time points from patients ≥ 12 years of age and shipped at ambient temperature to MoCha within 2 days for ctDNA analysis:

- Baseline
- C2D1
- C3D1 (± 3 days, or sooner if there is clinical evidence that the patient is responding to drug);
- at the first two restaging visits (end of C3 and end of C5);
- every two restaging visits after that (e.g., C9, C13, etc.); and
- at progression.

Blood specimens should be labeled with:

- Sample type (e.g., Whole blood)
- Time point (e.g., C1D1 pre dose)
- Collection date and time
- Sample ID, containing:
 - CTEP protocol number
 - Unique patient ID (Do NOT include patient name, medical record number, or initials)
 - 800-series sample collection number (e.g., 800, 801, 802, etc.)

For example, the sample ID for the baseline sample collected for NCI DTC patient #004 should be: 10398_NCIDTC_004_800.

Mononuclear cells will be isolated from whole blood by the MoCha Laboratory for nucleic acid extraction and exploratory WES to allow for germline and somatic variants to be accurately identified, and to enable the accurate assessment of mutational signatures in the tumor specimen and, possibly, cell-free DNA. The results of these studies will not be returned to patients.

Circulating tumor DNA (ctDNA) monitoring will be performed with the TSO500 assay and, potentially, WES. Patient plasma will be analyzed for ctDNA by the TSO500 panel and, if a sufficient proportion of the circulating, cell free DNA (cfDNA) is ctDNA, then WES of cfDNA will also be considered to uncover additional relevant changes in the tumor genome; the results of these studies will not

be returned to patients. Once a patient has come off study, ctDNA from blood samples correlating to clinically informative time points (minimally, before treatment and at restaging scans suggesting tumor growth) will be analyzed.

9.3.2 Pharmacodynamic Analysis – NCI Only

At **NCI only**, collection of blood samples for ImmunoPD studies will be mandatory for patients ≥ 12 years of age.

These samples will be used for the analysis of immune cell subsets and measurement of T-cell activation in the periphery. The activation status of peripheral T cell subsets will be determined based phosphomarker expression (pZAP70, pCD3 ζ , pSHP1/SHP2) assessed through intracellular staining and flow cytometry). These studies will allow us to follow changes in the T-cell population longitudinally and potentially correlate increases in T-cell activation with reduction in tumor burden.

9.3.2.1 Blood Sample Collection for ImmunoPD (NCI Only)

Blood samples (4 mL) will be obtained from patients ≥ 12 years of age at the following times:

- at baseline (on Cycle 1 Day 1 prior to drug administration)
- on Cycle 1 Day 15 (optional)
- on the first day of every subsequent cycle prior to drug administration
- at re-staging follow-up or disease progression

Per NIH Clinical Center CC Policy for pediatric patients, no more than 5 mL/kg may be drawn for research purposes in a single day, and no more than 9.5 mL/kg may be drawn over any eight-week period.

Samples will be collected into NaHep tubes (4 mL of blood into one 6 mL tube at each timepoint) and then added to 1x Lyse/Fix buffer per DCTD SOP LHTP003.08.15. Blood must be mixed with Lyse/Fix buffer within 5 minutes of collection. Once samples are processed, they should be stored in 60% methanol at -20°C for at least one hour (no longer than 6 hours) and then transferred to -80°C. **Please see DCTD SOP LHTP003.08.15 for detailed guidance.**

Materials for sample collection and processing will be provided to the clinic's sample collection team.

For NIH Clinical Center specimens only: At least 24 hours prior to blood sample collection, the research nurse will contact the NCI Phase I/II PK/PD Support Group in NIH Building 10: E-mail [contact], [contact] [contact] [contact].

9.4 Sample Collection and Processing

Biospecimens will be collected and processed using validated SOPs that will ensure both specimen quality (analyte preservation) and patient confidentiality pursuant to informed consent provisions. Information about each specimen (e.g., blood, tumor biopsy, per specific protocol) will be recorded on a PK/PD collection worksheet included in [Appendix E](#).

Using a computerized inventory system and a backup hardcopy process, all specimen collection and processing steps will be documented and the specific location of each specimen will be tracked. Each new specimen collected will be assigned a unique barcode identifier that can be linked to the original specimen collected and other relevant information within the inventory system. To ensure patient confidentiality, only containers used for the initial specimen collections will be labeled with patient identifiers.

Only the barcode identifier will be applied to all subsequent specimen containers. When specimens are processed and aliquoted, no patient information will be included on the new containers. Original specimen containers will be discarded. Only barcode-labeled specimens without patient identifiers will be shipped for analysis and/or storage. Specimen labels will indicate: CTEP protocol number, unique patient accession number, 3-digit sample number (see list below), collection time, and total volume collected, as appropriate. Samples from sets of at least three patients will be grouped for scientific analysis.

Standardized 3-digit sample collection numbers:

200 series: blood for PK

300 series: blood for PD

500 series: tumor biopsies

800 series: blood for genetic/genomic analyses

900 series: blood for ImmunoPD (NCI only)

The inventory process contains other security provisions sufficient to safeguard patient privacy and confidentiality. Access to the inventory system and associated documents will be restricted to appropriate individuals. Requests to use specimens stored in the repository must be approved. The only patient information available in the inventory system will be the patient sex, diagnosis,

and level of informed consent given. SOPs ensure that any changes in informed consent made by a patient and relayed to the PI will be reflected in the inventory system to ensure that specimens are destroyed as appropriate. All laboratory personnel will be trained to adhere to SOPs and will be monitored for high-quality performance.

Any new use of these samples will require prospective IRB review and approval. Access to these samples will only be granted following IRB approval of an additional protocol, granting the rights to use the material.

NCI patients participating in treatment protocols are often also enrolled on the NCI DTC longitudinal protocol, 17-C-0156, which enables transfer of a patient's research data and specimens longitudinally across multiple trials in which the patient has been enrolled. For NCI patients on the atezolizumab in CS and CCS study who are also enrolled on this longitudinal protocol, any frozen biopsy samples collected on this trial that are not needed to be used as the "baseline" tissue sample to determine the eligibility of the patient for a subsequent treatment-intent protocol (i.e., for which there is the possibility of direct benefit), can at the discretion of the PI be used for additional pharmacodynamic analysis to address questions about tumor responses to treatment. This affords us the opportunity to measure dynamic drug-specific target effects (e.g., changes in epithelial-mesenchymal transition, DNA damage response, or immune cell infiltration) in patients on consecutive clinical trials at the Developmental Therapeutics Clinic; there is tremendous value in being able to evaluate molecular changes before and during disease progression to understand why the tumors initially responded but then became resistant to treatment.

Patients on this study will not be consented to new use of their research tissue samples or informed of the results of these studies because (i) broad consent was obtained under the longitudinal protocol and (ii) there will be no direct benefit or added risk to the patient. No new samples will be collected on this study beyond those specified in the current protocol to meet the primary and secondary objectives. No information beyond that associated with the patient's longitudinal protocol registration ID will be shared with investigators performing the pharmacodynamic studies.

If at any time, a patient withdraws from the study and does not wish for their existing samples to be utilized, the individual must provide a written request. Following receipt of this request, the samples will be destroyed (or returned to the patient, if so requested), and reported as such to the IRB. Any samples lost (in transit or by a researcher) or destroyed due to unknown sample integrity (i.e., broken freezer allows for extensive sample thawing, etc.) will be reported as such to the IRB.

9.5 Privacy Considerations

As patient clinical response data (both for this study and, potentially, after a patient is off study) will be required for comparison to sequencing results, delinking the samples from identifying information is not feasible. A Certificate of Confidentiality has been obtained to help protect the privacy of all study participants. The informed consent document for this protocol contains language informing patients about the performance of genetic studies.

9.6 Management of Genomic Results

The results of the OCAv3 targeted sequencing assay performed by MoCha (under CLIA certification #21D2097127) on restaging follow-up or progression tumor biopsy tissue will be returned to patients in the Oncomine report.

Information regarding the Genomic Data Sharing Plan can be found in Section [12.6](#).

10. STUDY CALENDAR

Eligibility screening evaluations (see Section [3.3](#)) are to be conducted within 8 days prior to patient enrollment, with the exception of informed consent, echocardiogram (ECHO), and imaging, which must be done within 28 days prior to patient enrollment. Baseline history, physical examination, laboratory evaluations, and EKG are to be conducted within 8 days prior to the start of protocol therapy. If protocol therapy is started within 8 days of the eligibility screening evaluations, values from the screening evaluations may be used as baseline measurements; if >8 days have passed since the screening evaluations, the medical history, physical examination, laboratory evaluations, and EKG must be repeated prior to starting protocol therapy. Baseline imaging scans and ECHO must be done within 28 days prior to the start of protocol therapy.

Each cycle is 21 days (± 3 days due to scheduling conflicts). The start of a new cycle may be delayed up to 2 weeks to accommodate scheduling conflicts and other unexpected events. In the event that the patient's condition is deteriorating, laboratory evaluations should be repeated within 48 hours prior to initiation of the next cycle of therapy.

	Pre-Study Screening	Cycle 1 Week 1	Cycle 1 Week 2	Cycle 1 Week 3	Cycle 2 Week 1	Cycle 3 Week 1	Cycles 4+ Week 1	Off Treatment
Atezolizumab ^a		A			A	A	A	
Informed consent	X							
Demographics	X							
Medical history	X	X ^j						
Concurrent meds	X	X-----X						
Physical exam ^b	X	X ^j			X	X	X	X
Vital signs	X	X ^j			X	X	X	X
Height	X							
Weight	X	X ^j			X	X	X	X
Performance status	X	X ^j			X	X	X	X
CBC w/diff, plts ^c	X	X ^j			X	X	X	X
Serum chemistry ^c	X	X ^j			X	X	X	X
TSH ^d	X	X ^j			X	X	X	X
EKG ^e	X	X ^j						
Echocardiogram ^e	X	X ^j						
Adverse event evaluation		X-----X						X
Tumor measurements ^f	X	Tumor measurements are repeated every 6 weeks. Documentation (radiologic) must be provided for patients removed from study for progressive disease.						X
B-HCG ^g	X	X ^j			X	X	X	
Biopsy ^h		X				X ^h		X ⁱ
Blood for PD ^k		X		X ^k	X	X	X	X
Blood for genetics ^l		X	Blood for ctDNA analysis at C2D1, at the time of any biopsy, at the first two restagings (end of C3 and end of C5), and every two restaging visits after that (e.g., C9, C13, etc.)					X

a: Atezolizumab dose as assigned; adults ≥ 18 years at 1200 mg IV and in pediatric/adolescents ≥ 2 years at 15 mg/kg (max single dose=1200 mg); drug will be administered once on Day 1 only of each cycle. Each cycle is 21 days (± 3 days). Start of new cycle may be delayed up to 2 weeks to accommodate scheduling conflicts.

b: History and physical at baseline and up to 8 days before the start of each subsequent cycle.

c: CBC w/diff, plts, and serum chemistry (ACTH, albumin, alkaline phosphatase, AM cortisol, amylase, bicarbonate, total bilirubin, BUN, calcium, chloride, creatinine, glucose, LDH, lipase, phosphorus, potassium, pregnancy test per institutional standard at each participating site, total protein, SGOT [AST], SGPT [ALT], sodium, free T4) at baseline and then up to 3 days before the start of each subsequent cycle. After baseline, amylase, LDH, lipase, protein, and free T4 do not need to be checked.

d: TSH levels at baseline and then up to 3 days before the start of each subsequent cycle.

e: Baseline and as indicated.

f: CT scan or other imaging test at baseline, at the end of Cycle 3, and every two cycles thereafter (every 3 cycles for patients on study for >1 year; every 4 cycles for patients on study for >2 years).

g: Serum or urine pregnancy test (women of childbearing potential) within 8 days prior to enrollment. If

clinically indicated, serum or urine pregnancy test is required for women of childbearing potential ≤ 8 days before the start of each treatment cycle [per institutional standard at each participating site]; outside lab results are acceptable.

- h: Adult patients (≥ 18 years of age; mandatory at all sites), at baseline and prior to C3D1 (± 3 days) or sooner if there is clinical evidence that the patient is responding to drug, as described in Section [9.2.1](#).
- i: One optional tumor biopsy may be collected following progression or a 10-19% increase in tumor volume at restaging, as described in Section [9.2.1](#).
- j: Eligibility screening results may be used for these baseline measurements if conducted within 8 days (for medical history, physical exam, CBC, serum chemistry, TSH, and EKG) or 28 days (for ECHO) prior to the start of protocol therapy. See Sections [3.3](#) and [5](#).
- k: **At NCI only:** blood for ImmunoPD (mandatory from patients ≥ 12 years of age) on C1D1, C1D15 (optional), day one of each cycle, and at restaging follow up or progression as described in Section [9.3](#).
- l: At all sites, blood for genetic analysis is mandatory for patients ≥ 12 years of age. Two tubes at each of the following time points: baseline, C2D1, C3D1 (± 3 days, or sooner if there is clinical evidence that the patient is responding to drug); at the first two restagings (end of C3 and end of C5); every two restaging visits after that (e.g., C9, C13, etc.) as described in Section [9.3](#).

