- 3.3.3 Imaging Studies - every participant should have an evaluation of known sites of disease, conducted via a CT scan of the chest/abdomen/pelvis. This scan may be done at the enrolling institution; alternatively, images or reports from scans conducted at an outside institution may be used. Either way, the scan, image, or report used to determine eligibility must be *at least* as recent as the time of disease progression determination on the patient's last treatment. Scans for baseline tumor measurements must be done within 28 days prior to the start of protocol therapy; radiographs used to determine eligibility can be used for baseline measurements if the scans were conducted ≤ 28 days prior to start of protocol therapy and the site investigator determines that they are of acceptable quality. At the discretion of the PI and as clinically indicated, the following imaging studies may also be performed: MRI or CT scan with contrast of the brain, MRI liver, or MRI for other disease sites.
- 3.3.4 Laboratory Evaluation - laboratory data are to be obtained within 8 days prior to both enrollment and start of protocol therapy:
- Hematological Profile: CBC with differential, hemoglobin, platelets
 - Biochemical Profile: ACTH, albumin, alkaline phosphatase (ALP), AM cortisol, bicarbonate, total bilirubin, BUN, calcium, chloride, creatinine, glucose, LDH, phosphorus, potassium, total protein, SGOT [AST], SGPT [ALT], sodium, TSH, free T4, amylase, lipase
 - Urinalysis
 - Serum or urine pregnancy test for female participants of childbearing potential
 - PT and PTT only for patients undergoing research biopsies
- 3.3.5 Cardiac Evaluation
- EKG - to be performed within 8 days prior to both enrollment and start of protocol therapy
 - ECHO - to be performed within 28 days prior to both enrollment and start of protocol therapy

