5. TREATMENT PLAN

This is a multicenter open-label phase 2 trial evaluating atezolizumab in adult subjects ≥ 18 years of age and in pediatric/adolescent subjects ≥ 2 years of age with advanced CCS or CS. Patients will be divided into cohorts based on histology upon enrollment. There will be three cohorts: histologically confirmed CCS (or EWSR1 translocation), conventional CS (grade 2 or 3), and dedifferentiated CS.

Patient evaluations will be performed throughout the study as described below. Baseline history, physical examination, laboratory evaluations, urinalysis, and EKG are to be conducted within 8 days prior to the start of protocol therapy. If protocol therapy is started within 8 days of these eligibility screening evaluations (see Section [3.3](#)), values from the screening evaluations may be used as baseline measurements; if >8 days have passed since the screening evaluations, the medical history, physical examination, laboratory evaluations, urinalysis, and EKG must be repeated prior to starting protocol therapy. Baseline imaging scans and ECHO must be done within 28 days prior to the start of protocol therapy.

History and physical examination will be done within 8 days of Day 1 of all cycles. Labs (serum chemistries and CBC with differential) will be performed at baseline as described above, on Cycle 1 Day 15 [± 1 day], and then up to 3 days before the start of each subsequent cycle (LDH and protein do not need to be checked again after baseline). TSH will be checked at baseline (within 8 days of Cycle 1 Day 1) and then up to 3 days before the start of each subsequent cycle. EKG will be repeated as clinically indicated after the baseline measurement described above.

Patients will have a CT scan at baseline (within 28 days prior to start of protocol therapy). Patients will undergo a CT scan and be re-evaluated for response at the end of Cycle 3 and every two cycles thereafter (every 3 cycles for patients on study for >1 year; every 4 cycles for patients on study for >2 years). Given the concern of pseudoprogression ("tumor flare"), patients that are clinically well may continue on therapy following RECIST progression if they meet the criteria outlined in Section 11.4.

Research biopsies (mandatory for adult patients at all sites) and blood samples for PD studies (mandatory for patients ≥ 12 years of age) will be collected as described in Section [9.2](#) and Section [9.3](#).

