Symptoms of abdominal pain associated with elevations of amylase and lipase, suggestive of pancreatitis, have been associated with the administration of atezolizumab. The differential diagnosis of acute abdominal pain should include pancreatitis. Appropriate workup should include an evaluation for ductal obstruction, as well as serum amylase and lipase tests. Management guidelines for pancreatic events, including pancreatitis, are provided in the table below.

Event	Management
Amylase and/or lipase elevation, Grade 2	
Amylase and/or lipase $>1.5\text{--}2.0 \times \text{ULN}$:
 
 Continue atezolizumab. Monitor amylase and lipase weekly. For prolonged elevation (e.g., >3 weeks), consider treatment with corticosteroids equivalent to 10 mg/day oral prednisone. 
Asymptomatic with amylase and/or lipase $>2.0\text{--}5.0 \times \text{ULN}$:

Event	Management
	
 • Treat as a Grade 3 event.
Amylase and/or lipase elevation, Grade 3 or 4	
 • Withhold atezolizumab for up to 12 weeks after event onset.^a • Refer patient to GI specialist. • Monitor amylase and lipase every other day. • If no improvement, consider treatment with corticosteroids equivalent to 1–2 mg/kg/day oral prednisone. • If event resolves to Grade 1 or better, resume atezolizumab.^b • If event does not resolve to Grade 1 or better while withholding atezolizumab, permanently discontinue atezolizumab.^c • For recurrent events, permanently discontinue atezolizumab.
Immune-related pancreatitis, Grade 2 or 3	
 • Withhold atezolizumab for up to 12 weeks after event onset.^a • Refer patient to GI specialist. • Initiate treatment with corticosteroids equivalent to 1–2 mg/kg/day IV methylprednisolone and convert to 1–2 mg/kg/day oral prednisone or equivalent upon improvement. • If event resolves to Grade 1 or better, resume atezolizumab.^b • If event does not resolve to Grade 1 or better while withholding atezolizumab, permanently discontinue atezolizumab. • For recurrent events, permanently discontinue atezolizumab.

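### Section 5 and the study calendar set different on-treatment safety labs: the calendar has no Cycle 1 Day 15 panel and, on the natural reading, waives three more analytes after baseline

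*Combined protocol and SAP*

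**What the plan says.** **Section 5 (Treatment Plan).** "Labs (serum chemistries and CBC with differential) will be performed at baseline as described above, on Cycle 1 Day 15", with a window of one day either side, and again within the 3 days before every later cycle. A parenthesis adds that "LDH and protein do not need to be checked again after baseline". No other analyte is exempted. Section 5 does not list what its serum chemistries comprise, and it handles TSH in a separate sentence.

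**Section 10 (Study Calendar).** The CBC and serum chemistry rows are marked at screening, at week 1 of each cycle and off treatment. Neither has a mark under Cycle 1 Week 3. Footnote c lists the serum chemistry panel, which includes amylase, lipase and free T4, and schedules it thus: "free T4) at baseline and then up to 3 days before the start of each subsequent cycle". It then says: "After baseline, amylase, LDH, lipase, protein, and free T4 do not need to be checked".

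**Section 3.3.4 (screening labs).** The biochemical profile ends with "sodium, TSH, free T4, amylase, lipase".

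**Section 6.2 (pancreatic events).** One entry under Grade 2 begins "Asymptomatic with amylase and/or lipase" and covers values above 2.0 and up to 5.0 times the upper limit of normal. It sends the patient to Grade 3 handling: drug withheld for up to 12 weeks, referral to a GI specialist, and enzymes every other day.

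Nothing in the protocol says whether Section 5 or the calendar prevails.

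**The concern.** Sites often schedule visits from the calendar. Here the calendar requires less than the treatment plan on two counts.

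First, a site using the calendar alone does not draw the Day 15 chemistry and CBC. That is one of the two looks at transaminases, creatinine and blood counts that Section 5 places between the first and second doses.

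Second, such a site may stop amylase and lipase after baseline. Section 6.2 has a withholding rule for elevations without symptoms, but its table does not itself order routine testing. Without routine testing the rule can act only on results found for some other reason.

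At stake are safety monitoring and uniform practice across sites in a multicenter trial whose sites are audited against this text.

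**Working it through.** No power or sample-size figure is involved. The check compares the texts and counts days.

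**1. The two rules side by side**

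| Item | Section 5 | Calendar grid and footnote c |
|---|---|---|
| Chemistry/CBC on Cycle 1 Day 15 | Required, ±1 day | Not shown |
| Chemistry/CBC before each later cycle | Within 3 days | Within 3 days |
| Waived after baseline | LDH, protein (2) | LDH, protein, amylase, lipase, free T4 (5) |
| TSH before each later cycle | Yes | Yes |

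Difference in waived analytes: 5 − 2 = 3 (amylase, lipase, free T4).

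**2. Is the missing Day 15 entry a PDF artefact?** No. In the same grid the row for pharmacodynamic blood keeps its mark under Cycle 1 Week 3, so column positions survived. The wording of footnote c independently leaves Day 15 out.

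**3. Does Section 5's panel contain the three analytes?** This is inferred. Footnote c names all three within serum chemistry, and Section 3.3.4 includes them in its biochemical profile. Section 5 is not simply repeating the 3.3.4 list, however, because 3.3.4 places TSH inside that profile while Section 5 treats TSH separately. Footnote c's own list is the better support.

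**4. Post-dose checks before dose 2.** Section 5: Day 15 plus pre-Cycle 2 = 2. Calendar: pre-Cycle 2 only = 1.

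**5. Day of the first post-dose check** (Cycle 1 Day 1 = day 1)

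- Nominal schedule: Section 5 gives day 15. Cycle 2 starts on day 1 + 21 = 22, and labs up to 3 days before fall on day 19–22. Gap: 19 − 15 = 4 to 22 − 15 = 7 days.
- With visit windows: Section 5 gives day 14–16. The calendar says "Each cycle is 21 days (± 3 days due to scheduling conflicts", so Cycle 2 starts on day 19–25 and labs fall on day 16–25. Gap: 16 − 16 = 0 to 25 − 14 = 11 days.

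**6. How many patients could have an enzyme elevation?** The risk list in Section 7.1 (n = 3097) marks lipase increased and serum amylase increased as below 3%. Section 13.2 sets the accrual ceiling at 68.

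- Per analyte: less than 0.03 × 68 = 2.04, about 2 patients or fewer.
- If the two never occurred in the same patient: less than 2 × 2.04 = 4.08, about 4.
- Asymptomatic elevations at the withholding level are a subset of these.

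This assumes that the pooled rate carries over to this trial. That rate itself depends on how often the pooled studies tested the enzymes, which the protocol does not say.

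**The case against.** The strongest reply is that the two texts can be followed together. The calendar does not forbid a Day 15 draw, and footnote c permits omission rather than ordering it. A site doing the Section 5 labs complies with both, and footnote j already refers readers to Section 5, though for baseline measurements. This stands: the texts do not make compliance impossible. The problem lies in one direction only, for a site that works from the calendar.

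Safeguards under either text are also substantial: CBC, chemistry and TSH before each dose, history and physical examination each cycle, repeat labs within 48 hours of the next cycle if the patient is deteriorating, and symptom-driven enzyme and thyroid testing under Section 6.2. A reader might infer that dose 2 could be given without any post-dose safety labs. The documents do not support that, because the pre-cycle draw is required in both places.

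A reader might also infer a much longer gap from the calendar's allowance that "The start of a new cycle may be delayed up to 2 weeks to accommodate scheduling conflicts and other unexpected events". Two weeks added to nominal day 22 gives day 36, with labs on day 33–36, which is 33 − 16 = 17 to 36 − 14 = 22 days after the Section 5 draw. But dose 2 is postponed by the same delay, so this does not measure added exposure without monitoring.

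Finally, footnote c names amylase and lipase explicitly, which may reflect a deliberate choice by the sponsor. If so, Section 5 was not brought into line. That is a reason to leave the choice of waiver with the sponsor, not a reason to leave the texts different.

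**Conclusion.** The discrepancy is real, and it is a minor safety-monitoring inconsistency. The Day 15 difference is plain from the text. The three-analyte difference rests on reading Section 5's serum chemistries as the panel that footnote c lists, which is likely but not stated.

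For a site using the calendar alone, the cost is one of two post-dose checks before dose 2 and a first check nominally 4–7 days later. Withhold-level enzyme elevations without symptoms would be found only incidentally. The number of such patients is likely to be very small, subject to the carry-over assumption above. The documents do not support reading this as a threat to the trial's conclusions: the objective response analysis does not use these labs.

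**What to change.** State one lab rule in identical words in Section 5, the calendar grid and footnote c.

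1. **Day 15.** Add the chemistry and CBC that Section 5 already requires to the Cycle 1 Week 3 column and to footnote c. Cost: possibly an extra visit at sites now following the calendar, since the only Day 15 draw the calendar shows is an optional research sample at the NCI.
2. **Waiver list.** Use one post-baseline list in both places. The sponsor chooses between two options:
   - Keep amylase, lipase and free T4 on the pre-cycle draws already scheduled. Cost: three more assays per draw, and more asymptomatic enzyme findings leading to drug holds, GI referral and every-other-day enzyme testing.
   - Waive them in both places, and state in the Section 6.2 pancreatic table that its asymptomatic entry covers incidental results. Cost: silent elevations go undetected unless found by chance.

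The change is otherwise a wording amendment with no effect on sample size or analysis.
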